6. ENDPOINTS AND COVARIATES

There is no formal hypothesis testing therefore endpoints are not designated as primary or secondary.

In general, the baseline value will be defined as the last non-missing value prior to first dose from B1871008 and B1871006, unless specifically stated otherwise. Assessments performed on Week 1 day 1 will be assumed to be pre-dose per the schedule of activities in the Protocol.

An on-treatment efficacy evaluation is defined as any evaluation done during bosutinib therapy or within 30 days of last dose for B1871008 patients and up to date of treatment discontinuation for B1871006 patients. An on-treatment safety evaluation is defined as any evaluation done during bosutinib therapy or within 30 days of last dose.

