Molecular response in B1871006 was based on the difference between the subject's change in Bcr-Abl/Abl ratio and a laboratory reference baseline. The Quest (vendor) laboratory reference Bcr-Abl/Abl ratio of 4.1325 derived from a pool of 120 previously untreated CML subjects was used as the standardized (or reference) baseline. Molecular response was not analyzed for subjects in China, India, the Russian Federation, and South Africa due to logistical constraints in transporting samples to the central laboratory.

To be considered a responder for MMR in B1871006, a subject must have had at least a 3-log reduction from the Quest standardized baseline, a detectable Bcr-Abl transcript at baseline or any time post-baseline, and must have maintained or attained a CCyR. Additionally, as a conservative approach given the known variability with standard MMR analyses, a subject who had a non-CCyR on the same day as the MMR assessment was not considered to have a MMR at that time point. MR⁴ was defined similar to MMR except at least a 4-log reduction was required. In B1871040, responders had MMR/MR⁴ or better denoted on the CRF as assessed by a local laboratory. On-treatment response is independent of a patient's baseline molecular response.

PFS is defined as the time from first dose to progression as assessed by the investigator and noted as the reason for permanent treatment discontinuation on the CRF or on-treatment death due to any cause ($[\text{date of progression/death} - \text{first dose date}]/30.4$), whichever occurs first. Patients without events are censored at the last cytogenetic, hematologic, or laboratory assessment where progression could be assessed. Progression for B1871006 patients is defined as:

- *Evolution from chronic phase (or from return to chronic phase for advanced subjects) to accelerated phase or blast crisis (on two consecutive assessments at least a week apart).*
- *Evolution from accelerated phase to blast crisis (on two consecutive assessments at least a week apart).*
- *One of the following conditions occurring after dose escalation or presence of adverse events prohibiting dose escalation:*
 - *For 2nd or later line subjects, loss of major cytogenetic response (need at least 30% increase).*
 - *For all lines of treatment, loss of complete hematologic response confirmed by 2 assessments at least 2 weeks apart.*

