 - *For all lines of treatment, increasing WBC defined as doubling of WBC, occurring over a period of ≥ 1 month, with the second WBC $> 20 \times 10^9/L$ and confirmed at least 1 week later.*

For DOR and PFS, if there is an unacceptable gap between the date of progression or death and the date of the most recent prior disease assessment (>48 weeks), the event will not be used and censorship will be at the most recent prior assessment.

Transformation, defined by the first two progression bullets above, is the time from first dose to confirmed transformation ($[\text{date of transformation} - \text{first dose date} + 1]/7$). Confirmed transformation is defined as 2 consecutive assessments at least 1 week apart or 1 assessment confirmed by progression of disease or death. Patients without events are censored at the last hematologic or extramedullary assessment where transformation could be assessed.

BCR-ABL mutational status at treatment discontinuation will be assessed. Emergent mutations are defined as those mutations which were not present at baseline. B1871006 patients who were not assessed for baseline mutations are not assessable for emergent mutations. All B1871008 patients are assessable for emergent mutations.

OS is defined as the time from randomization for B1871008 patients and from first dose B1871006 patients to the date of death ($[\text{date of death} - \text{randomization/first dose date}]/30.4$). Patients who have not died will be censored at the last known alive date.

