8.2.1. Analysis of Efficacy Endpoints

The duration of cytogenetic, hematologic, and molecular response analyses are based on the full analysis set for the subset of B1871006 patients who respond for the respective endpoint. The K-M method, as described in [Section 8.1](#), will be used provided most responding patients transferred to B1871040 remain on treatment until progression or loss of response. The percentage of MR⁴, MMR, MCyR, CCyR, and PCyR and CHR and major hematologic response (MHR)/OHR (advanced patients only) for the respective endpoint, along with confirmed losses and censored patients still on-treatment will be summarized.

The time to transformation analysis is based on the full analysis set for the B1871006 patients. Cumulative incidence of transformation adjusting for the competing risk of treatment discontinuation due to any reason without transformation, as described in [Section 8.1](#), will be used. The percentage of transformation without treatment discontinuation and the percentage of treatment discontinuation due to any reason without transformation will be summarized. The specific disease stage transformation (accelerated or blast phases) will also be listed.

The PFS analysis is based on the full analysis set for the B1871006 patients. The K-M method, with or without unsatisfactory response as assessed by the investigator as an event and cumulative incidence of on-treatment progression or death adjusting for the competing risk of treatment discontinuation due to any reason without the event, as described in [Section 8.1](#), will be used. For K-M, the percentage of on-treatment death or progression, with or without unsatisfactory response as an event, will be summarized. For cumulative incidence, the percentage of on-treatment death or progression without treatment discontinuation and the percentage of treatment discontinuation due to any reason without on-treatment progression and death will be summarized.

The OS analysis is based on the full analysis set for all patients. The K-M method, as described in [Section 8.1](#), will be used. The number of deaths and causes of death will be summarized. Time on study from date of randomization for B1871008 patients and date of first dose for B1871006 patients to date of last contact, and reasons for discontinuing participation will also be summarized.

The percentage of patients with emergent mutations will be summarized.

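### A confirmed AP/BP transformation can be left out of PFS when progression is not the CRF reason for stopping bosutinib

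*SAP*

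**What the plan says.** SAP 6.1 sets two conditions for a progression to count in PFS, joined by *and*: it must be "progression as assessed by the investigator and noted as the reason for permanent treatment discontinuation on the CRF". The alternative event is on-treatment death. For everyone else, "Patients without events are censored at the last cytogenetic, hematologic, or laboratory assessment where progression could be assessed".

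The same section then lists what progression means for B1871006 patients. The first criterion is "Evolution from chronic phase (or from return to chronic phase for advanced subjects) to accelerated phase or blast crisis", and the second is evolution from accelerated phase to blast crisis. Both need two consecutive assessments at least a week apart.

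The transformation endpoint reuses those criteria: "Transformation, defined by the first two progression bullets above, is the time from first dose to confirmed transformation". Confirmation is by two consecutive assessments, or by one assessment followed by progression or death. The CRF stop reason plays no part.

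Three other rules matter:

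- SAP 6 ends the on-treatment efficacy window "up to date of treatment discontinuation for B1871006 patients".
- SAP 6.1 has a 48-week gap rule, opening "For DOR and PFS, if there is an unacceptable gap between the date of progression or death", which is not applied to transformation.
- SAP 8.2.1 analyses PFS in two ways. Kaplan-Meier is run "with or without unsatisfactory response as assessed by the investigator as an event". Cumulative incidence treats discontinuation as a competing risk, and "the percentage of treatment discontinuation due to any reason without on-treatment progression and death will be summarized".

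**The concern.** AP/BP evolution is part of the definition of progression, so every confirmed transformation on treatment would be expected to be a PFS event as well, apart from those removed by the gap rule. Under SAP 6.1 this need not be so, because an administrative field, the reason recorded for stopping, decides whether the disease event counts.

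The omission runs in one direction. Censoring a patient at or near a transformation is informative and raises Kaplan-Meier PFS. Counting the patient as a competing discontinuation lowers the cumulative incidence of progression or death. One patient can then appear as transformed in one table and progression-free in another. The study tests no hypotheses, so these estimates are themselves the result, and PFS is a named endpoint in both documents.

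**Working it through.** The documents state no sample size, power or PFS target for this study, so there is no figure to reproduce. The check is first logical, then one of scale.

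**Step 1: apply the rules.** Take a B1871006 patient who meets either AP/BP criterion on two consecutive on-treatment assessments at least a week apart. Set the gap rule aside.

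| What happens next | Transformation | Kaplan-Meier PFS | Cumulative-incidence PFS |
|---|---|---|---|
| Stops; CRF reason is progression | Event | Event | Event |
| Stops; CRF reason is an AE or patient request; no on-treatment death | Event | Censored | Discontinuation without the event |
| Stops; CRF reason is unsatisfactory response; no on-treatment death | Event | Censored; event only in the variant | Discontinuation without the event |
| Stays on drug; later stops for progression or dies on treatment | Event | Event | Event |
| Stays on drug; neither occurs later | Event | Censored | No event |

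Rows 2, 3 and 5 are the discordant ones. The Kaplan-Meier variant repairs row 3 only, and SAP 8.2.1 specifies no such variant for cumulative incidence. A death after stopping does not restore the event if on-treatment death follows the same window as on-treatment efficacy evaluations. The SAP does not define on-treatment death, so that is an assumption.

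**Step 2: who can be affected.** Chronic- and accelerated-phase patients can meet a criterion directly. A blast-phase patient can do so only after return to chronic phase.

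**Step 3: effect per patient, cumulative incidence.** Inputs from Protocol 1.2.2: 288 second-line chronic phase, 164 advanced (accelerated phase, blast phase and Ph+ ALL pooled) and 570 treated in B1871006. The total agrees with 560 patients being reported as 98%: 560/570 = 98.2%. By subtraction, third- and fourth-line chronic phase is 570 − 288 − 164 = 118.

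With little censoring on treatment before the time point, cumulative incidence is close to events/N. Moving one patient from competing event to event therefore adds 1/N:

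- 100/288 = 0.35 points
- 100/118 = 0.85 points
- 100/164 = 0.61 points

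The low-censoring condition is plausible at 10 years. SAP 8.2.1 says that all but one of the patients enrolled in the extension had reached 10 years before the March 2020 anchor date.

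**Step 4: effect per patient, Kaplan-Meier.** An extra event with n at risk multiplies later survival by (1 − 1/n), a drop of S/n. Take S = 0.806, the second-line Year 2 PFS in Protocol 1.2.2. The documents do not give n, so it is assumed:

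- n = 200: 0.806/200 = 0.4 points
- n = 100: 0.806/100 = 0.8 points
- n = 50: 0.806/50 = 1.6 points

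**Step 5: direction and shape, on assumed rates only.** Suppose constant yearly hazards of 0.02 for transformation, 0.08 for other progression and 0.20 for other discontinuation, and let a share s of transformations carry another stop reason. Then 10-year Kaplan-Meier PFS is exp[−10 × (0.10 − 0.02s)]. The 10-year cumulative incidence is (0.10 − 0.02s)/0.30 × (1 − e^−3).

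| s | Kaplan-Meier PFS | Cumulative incidence |
|---|---|---|
| 0 | 36.8% | 31.7% |
| 0.10 | 37.5% | 31.0% |
| 0.25 | 38.7% | 30.1% |
| 0.50 | 40.7% | 28.5% |

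None of these hazards or shares comes from the documents. The table shows the direction and how the error grows with s.

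**The case against.** The best defence is Protocol 5.3. It lists the same two AP/BP criteria as disease progression for which bosutinib should be stopped. A patient managed by the protocol stops for progression, and the SAP rule then counts the event. Discordance needs a departure from 5.3 or a different entry on the CRF, and nothing shows that even one such patient exists. We also cannot see whether the CRF takes one reason or several. This stands as an argument that cases are few. It does not close the gap: 5.3 says what should happen and does not fix the recorded reason when, say, toxicity and transformation coincide. The separate unsatisfactory-response label shows that efficacy failure can be recorded under a name other than progression.

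It is also fair that transformation, duration of response and overall survival are reported separately, that listings of efficacy data and stop reasons are planned, and that no decision rule depends on PFS. These points limit the harm but do not correct the PFS estimates.

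Several stronger readings are tempting and are not supported:

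- **A breach of Protocol 9.5**, which has no stop-reason condition. Protocol 9 allows the SAP to modify the protocol's plans. The problem is that two endpoints in one SAP disagree about the same disease event.
- **PFS events are dated late.** The formula uses the date of progression and does not say whether that is an assessment date or a CRF date.
- **Everyone who stays on drug after transforming is lost.** A later stop for progression or an on-treatment death still counts.
- **The AE discontinuations in Protocol 1.2.2 measure the problem.** Their leading causes were thrombocytopenia, raised ALT and neutropenia, and nothing links them to AP/BP.

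**Conclusion.** The inconsistency is real and follows from the SAP's wording alone. A confirmed on-treatment AP/BP evolution can be a transformation event yet be censored in Kaplan-Meier PFS, or tabulated as discontinuation without the event in cumulative-incidence PFS. No planned PFS version fully repairs it. Any bias favours PFS.

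Its total size cannot be derived from the documents, and Protocol 5.3 suggests that it is small. What can be stated is the scale per patient: about 1/N in cumulative incidence (0.35 points for N = 288) and S/n in Kaplan-Meier, with n assumed. A reader might infer that PFS is materially overstated, but that would need a count of discordant patients, which neither document gives.

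The cumulative-incidence figure rests on little on-treatment censoring before 10 years. The statement that a later death does not restore the event rests on reading on-treatment death by the SAP 6 efficacy window. Given the low cost of the remedy, the SAP should be changed.

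**What to change.** In SAP 6.1 and 8.2.1, add a PFS version, for both Kaplan-Meier and cumulative incidence, whose event is the earliest of:

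- (a) AP/BP evolution on treatment, shown on two consecutive assessments at least one week apart as in the existing progression criteria, whatever the CRF stop reason;
- (b) investigator-recorded progression leading to discontinuation;
- (c) on-treatment death, with that term defined.

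Do not carry over the transformation endpoint's alternative of one assessment confirmed by progression or death. That death is not limited to treatment, so a single reading could become a PFS event. Keep the 48-week gap rule for PFS. It does not apply to transformation, so some differences between the two endpoints will remain and can be explained. Leave the escalation-dependent criteria with the investigator.

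Report the existing CRF-reason version alongside, for continuity with the parent-study reports. List every patient whose PFS status or date differs between the versions, with the CRF stop reason.

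The cost is one extra derivation from assessments already collected, one table and one listing. The drawback is that PFS in the added version may be slightly lower than in earlier reports, which is why both versions should be shown.

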- To collect long-term safety and efficacy data for bosutinib;
- To assess the duration of clinical benefit for Ph+ CML patients treated with bosutinib;
- To fulfill the EMA post-approval requirement for the collection and analysis of safety data about diarrhea incidence after switch from clinical study to commercial bosutinib formulation.

Endpoints:

The objective of the study is to provide long-term access to bosutinib treatment and assess long-term safety, tolerability and duration of clinical benefit, without any formal hypothesis testing; therefore, there is no formal primary endpoint. In addition, data to be collected are planned to be different in the first line CP patients relative to the later line and advanced patients. For all patients regardless of the line of treatment:

For all patients:

- Long-term safety of bosutinib, including type, incidence, severity, timing, seriousness and relatedness of adverse events (AEs) and laboratory abnormalities as well as reason of treatment discontinuation. A special focus will be made on diarrhea in order to satisfy the EMA post-commitment request;

- BCR -ABL mutations present at the time patients discontinue Bosutinib. (Samples collected for all patients except those enrolled at sites in China)
- Overall survival (OS);
- Fulfill the EMA post-approval requirement to compare the pharmacokinetic analysis of C_{trough} of bosutinib in this study to C_{trough} of previous studies. (Samples collected for all patients except those enrolled at sites in China)

For 2nd or later line patients coming from study B1871006 who are still on treatment with bosutinib, the following efficacy endpoints will be assessed ([Appendix 1](#)):

- Duration of hematologic and cytogenetic responses;
- Progression-free survival;
- Time to transformation to accelerated or blast phase.

Study Design:

This is an open-label bosutinib treatment extension protocol. This protocol will be offered to those bosutinib patients who were previously enrolled in one of the two parent CML bosutinib studies (B1871006 or B1871008).

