2.2. Endpoints

The objective of the study is to provide long-term access to bosutinib treatment and assess long-term safety, tolerability and duration of clinical benefit, without any formal hypothesis testing; therefore, there is no formal primary endpoint.

In addition, data to be collected are planned to be different in the first line CP patients relative to the later line and advanced patients.

For all patients regardless of the line of treatment:

- Long-term safety of bosutinib, including type, incidence, severity, timing, seriousness and relatedness of AEs and laboratory abnormalities as well as reason of treatment discontinuation. A special focus will be made on diarrhea in order to satisfy the EMA post-commitment request;
- BCR -ABL mutations present at the time patients discontinue Bosutinib.
(For all patients except those enrolled at sites in China)
- Overall survival (OS);
- Fulfill the EMA post-approval requirement to compare the pharmacokinetic analysis of C_{trough} of bosutinib in this study to C_{trough} of previous studies.

For 2nd or later line patients coming from study who are still on treatment with **bosutinib**, the following efficacy endpoints will be assessed ([Appendix 1](#)):

- Duration of hematologic and cytogenetic responses;
- Progression free survival;
- Time to transformation to accelerated or blast phase.

Refer to [Section 7.1.1](#) for more details on endpoint definitions.

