9. DATA ANALYSIS/STATISTICAL METHODS

Detailed methodology for summary and statistical analyses of the data collected in this study will be documented in a Statistical Analysis Plan, which will be maintained by the sponsor. This document may modify the plans outlined in the protocol; however, any major modifications of the endpoint definition and/or its analysis will also be reflected in the clinical study report.

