9.3. Overall Survival

Overall survival (OS) or survival time is defined as the interval from the date of randomization (first line patients enrolled from B1871008) or first dosing (second or later line patients enrolled from B1871006) in the parent study to the date of death due to any cause. Patients not known to have died are censored at the last known alive date. OS will be calculated for all patients enrolled in the parent study B1871008 and dosed in the parent study B1871006.

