9.4. Time to Transformation to AP/BP

Time to transformation is defined as the time from the date of first dose in the parent study to the first date of confirmed transformation to AP or BP. For patients without transformation, censorship is at the last evaluation date.

Time to transformation will be calculated only for patients in 2nd or plus line setting while on treatment.

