9.5. Progression-Free Survival

Progression-free survival (PFS) is the interval from the date of first dose of bosutinib in the parent study until the earlier date of progression or death from any cause. Patients without events are censored at the last evaluation date.

PFS will be calculated only for patients in 2nd or above line setting.

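### The SAP's PFS counts only on-treatment deaths while protocol 9.5 counts all deaths, and in the extension a PCR result can create or maintain a CCyR but cannot count towards its loss

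*SAP*

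**What the plan says.** **PFS.** Protocol 9.5 measures from first dose "until the earlier date of progression or death from any cause", and "Patients without events are censored at the last evaluation date". It carries no on-treatment limit. Section 9.4, just before it, does: "Time to transformation will be calculated only for patients in 2nd or plus line setting while on treatment". The protocol is not uniform, because the Summary (Endpoints) introduces PFS for later-line patients "who are still on treatment with bosutinib, the following efficacy endpoints will be assessed", and Section 2.2 has a similar restriction. SAP 6.1 counts investigator-assessed progression "noted as the reason for permanent treatment discontinuation on the CRF or on-treatment death due to any cause". SAP 8.2.1 plans Kaplan-Meier with and without unsatisfactory response as an event, and cumulative incidence with discontinuation as the competing risk. All three use on-treatment events. SAP 6.1 also discards a progression or death that falls more than 48 weeks after the latest disease assessment.

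Protocol 9 lets the SAP modify the plan, adding that "any major modifications of the endpoint definition and/or its analysis will also be reflected in the clinical study report".

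**CCyR duration.** Protocol 7.1.1 allows RT-PCR in place of cytogenetics once molecular response is reached, and Section 6.3 extends this to the end-of-treatment visit. SAP 7 allows a CCyR to be imputed in B1871040 on a date with MMR or better. It prefers same-date conventional cytogenetics with at least 20 metaphases to PCR, but PCR to discrepant FISH. Under SAP 6.1, confirmed CCyR loss needs two assessments at least 28 days apart showing Ph+ metaphases or FISH at 1% or more, or else progression or death. Patients without confirmed loss are censored at the last assessment at which response could be judged.

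**The concern.** Both points concern what a published curve means. The study has no hypothesis test and no primary endpoint, so the definitions carry the interpretation.

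A reader who takes PFS from protocol 9.5 expects a death after stopping bosutinib to be an event. Under the SAP that patient is censored, or in the cumulative-incidence analysis has the competing event. No planned PFS analysis shows the other version, although survival is followed after discontinuation. Nor does OS fill the gap, because it ignores progression. The window for an on-treatment death is also left open: SAP 6 ends B1871006 efficacy at discontinuation, while its safety rules use 30 days.

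For CCyR the rules are one-sided. PCR can supply the response or keep it going, but a PCR result worse than MMR has no cytogenetic meaning. A patient followed only by PCR who loses CCyR is censored unless the loss shows up as progression, death or a later cytogenetic test. A fall from complete to partial response is not in itself progression, because the SAP's cytogenetic criterion asks for loss of major response. In B1871006 the same-day precedence ran the other way: a non-CCyR cancelled an MMR, which the SAP calls conservative.

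**Working it through.** The documents give no figure to reproduce for either point.

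**PFS, size under stated assumptions**

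Inputs for second-line chronic phase (protocol 1.2.2, n=288): 2-year PFS 80.6%, 2-year OS 90.6%. Section 1.2.2 does not say that this PFS is on-treatment; using it so is an assumption.

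- On-treatment event rate: a = -ln(0.806)/24 = 0.00899 per month.
- Overall death rate, for orientation: -ln(0.906)/24 = 0.0041 per month.
- Assumed, not in the documents: stopping without an event c = 0.01 to 0.03 per month; death after stopping b = 0.004 to 0.02 per month; constant rates; no progression recorded after stopping.
- 5-year on-treatment PFS (Kaplan-Meier): exp(-60a) = 58.3%.
- Any-death PFS, censored at the last known alive date: exp(-(a+c)t) + [c/(a+c-b)] × [exp(-bt) - exp(-(a+c)t)], with t = 60.

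| c | b = 0.004 | b = 0.009 | b = 0.02 |
|---|---|---|---|
| 0.01 | 63.1% | 58.3% | 50.6% |
| 0.02 | 66.5% | 58.3% | 45.5% |
| 0.03 | 68.8% | 58.3% | 42.0% |

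The range is 42-69%. It crosses the on-treatment value where b equals a, so the direction depends on whether patients die faster after stopping than they have events on treatment. The documents do not settle that.

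The 48-week rule could not sensibly apply to this version. Scheduled efficacy assessments end with treatment (protocol 7.1.1). In the same model, 74-86% of post-stopping deaths within 10 years of first dose fall more than 48 weeks after stopping and would be removed.

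**CCyR, the rules side by side**

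| Results on a B1871040 date | Status under SAP 6.1 and 7 |
|---|---|
| PCR only, MMR or better | CCyR may be imputed |
| PCR only, worse than MMR | No cytogenetic result |
| FISH at 1% or more, with MMR or better | CCyR may be imputed; the FISH result is displaced |
| Marrow with at least 20 metaphases, any PCR | Marrow result stands |

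No row turns PCR into an assessment that counts towards loss.

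**CCyR, size under stated assumptions**

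Only B1871040 visits are affected. SAP 8.2.1 says all enrolled patients but one reached 10 years before 11 March 2020, so they started before about 11 March 2010. The original extension protocol is dated 25 February 2013, at least 2.96 years after first dose. Amendment 1, which brought in the allowance for local PCR, is dated 10 August 2016, at least 6.4 years after.

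Assume response at month 6 and look seven years after response. The unaffected time is then u = 2.96 - 0.5 = 2.46 years, or u = 6.4 - 0.5 = 5.9 years. With loss rate L per year, PCR-only share m, and share q of their losses recorded another way (all assumed):

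- True retention: exp(-7L).
- Planned curve: exp(-L·u - L(1 - m(1-q))(7 - u)).

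| L, m, q | True | u = 2.46 | u = 5.9 |
|---|---|---|---|
| 0.01, 0.3, 0.8 | 93.2% | 93.5% (+0.3) | 93.3% (+0.1) |
| 0.03, 0.5, 0.5 | 81.1% | 83.9% (+2.8) | 81.7% (+0.7) |
| 0.05, 0.8, 0.5 | 70.5% | 77.2% (+6.7) | 72.0% (+1.6) |

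Differences are in percentage points, from unrounded values. With m = 0 or q = 1 the difference is zero. A response later than month 6 would leave more of the seven years exposed.

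**The case against.** **On PFS.** The SAP is entitled to differ: protocol 9 says so, and the Summary and Section 2.2 already tie PFS to patients still on treatment. The SAP states its definition openly, plans a competing-risk analysis, and captures all deaths in OS. Its list of changes compares SAP versions, so silence there proves nothing. All of this stands, and a reader who inferred a breach of the protocol would be wrong. What remains is that 9.5 and the SAP give one endpoint name to two events, and the SAP does not say so.

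A reader might also infer that the SAP's curve flatters bosutinib. The table does not support that, because the any-death figure falls on either side. Applying 9.5 literally, with survivors censored at a last evaluation taken as the stopping date, would always give a lower curve. That is by construction, since it adds deaths without the follow-up time of those who survive, so it is not evidence of bias in the SAP.

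**On CCyR.** One-way imputation has a rationale. MMR in B1871006 required a CCyR, whereas nothing in the documents equates loss of MMR with loss of CCyR. The imputation is permissive, marrow results prevail over PCR, and duration of MMR and MR4 is analysed with PCR-based loss rules. Protocol 9.6 lists MCyR, CHR and OHR but not CCyR. These points limit the matter; they do not let a PCR-only patient count as a CCyR loss.

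A reader might apply the PCR-only share from the day of response. With u = 0 the same formula gives 4.4 points in the middle case and 10.6 in the highest. The documents do not support this, because the imputation covers extension visits only.

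**Conclusion.** Both points hold on the written text and deserve correction, though neither touches a hypothesis test.

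For PFS the finding is an unflagged difference in the death event, with the protocol itself mixed. Its size and direction cannot be read from the documents: 42-69% against 58% at five years, under assumed stopping and post-stopping death rates.

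For CCyR duration the expected direction is upward in PCR-only patients. The size is about 2.8 points (middle case) to 6.7 (highest) if PCR-only monitoring began when the extension opened, and 0.7 to 1.6 if it began with Amendment 1. Loss rate, PCR-only share and the share of losses recorded another way are all assumed. The documents do not give the PCR-only share, so the effect could be negligible.

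**What to change.** **PFS**

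- Reconcile the protocol Summary, 2.2 and 9.5 with SAP 6.1 and 8.2.1.
- Name the SAP endpoint on-treatment PFS, state its death window, and record the difference in the study report.
- Add one descriptive any-death PFS, exempt from the 48-week rule and censored as protocol 9.3 does for OS: "Patients not known to have died are censored at the last known alive date".
- Footnote that progression after stopping is not systematically assessed, and that deaths may be unknown for patients who did not re-enrol.
- Do not add a curve that applies the 9.5 censoring literally.

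**CCyR duration**

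- Add a sensitivity analysis in which the SAP's own confirmed loss of MMR (two results at least 28 days apart, one at MR1 or worse) ends an imputed CCyR.
- Add a second in which PCR does not override a same-day FISH non-CCyR.
- Report the share of B1871040 response assessments that are PCR-only.
- Leave MCyR as planned.

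**Cost.** SAP wording and three descriptive runs; the CCyR runs use data already on the CRF. The any-death PFS is only as complete as survival follow-up, and it treats living patients with unrecorded progression as progression-free. Loss of MMR is only a proxy for loss of CCyR, so it belongs in a sensitivity analysis and should not replace the planned rule.
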